described and secured by a process inspired by a previously used prospective effect and process evaluation [47].

Table of interventions, methods, personnel resources, setting and frequency

Interventions in the existing setting	Method	Personnel requirements	Work flow and setting	Frequency
Patient education by the doctors	Education	Doctors	Existing setting and work flows are used and systematized	During the primary rehabilitation
Education cafe	Education	Interdisciplinary		
Education of the relatives	Education	Interdisciplinary		
Cardiovascular exercise and wheelchair skills sessions	Education/ practical	Physiotherapists		
Occupational therapy	Education/practice/goal setting	Occupational therapists		
The Hospital kitchen	Supervision and guidance related to diet composition	Kitchen staff		
Meetings for goal setting	Meeting between the patient and the interdisciplinary health care professionals	Interdisciplinary	Existing setting and work flows are used and systematized	every 14 days
Interventions beyond the existing setting	Method	Personnel requirements	Work flow and setting	Frequency
Education of the health care personnel	Education	Ph.D student + in- and external teachers	All health care personnel	Same lecture x 2 or more before the intervention
Patient Decision Aids	Patient Decision Aids related to physical activity and healthy diet s + use of mentors with SCI	Interdisciplinary	Developed from the existing template	Early stage after admission
Motivational counseling	One session during primary rehabilitation	Selected health care providers with expertise	Provided time and setting	Early stage after admission
Test and outcome measures	Method	Personnel requirements	Work flow and setting	Admission* Discharge* Follow up* After terminated Ph.D project*

Oxygen uptake	VO2peak test	Ph.D student**	Exercise test	X
Objective PA	Accelerometer	Ph.D student**	-	X
Bodyweight	Weighing	Nurses	Existing	X
Body composition	Dexa scan	Secretaries/doctors	Glostrup Hosp.	X
Metabolic profile	Blood sample	Nurse/doctor/secretary	Existing	X
Level of functioning	SCIM	Interdisciplinary	Existing	X
Neurological status	ISNCSCI	Physiotherapists	Existing	X
Depression	Questionnaire	Doctors (admission)#	Existing	X
Quality of Life	Questionnaire	Nurses (discharge)#	Existing	X
Self - reported physical activity	Questionnaire	Ph.D student	-	X
Self- assessed ability to be physically active	Questionnaire	Ph.D student	-	X
Measure of patient participation /shared decision	Questionnaire	Ph.D student	-	X

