Measure for a varied and healthy diet in an appropriate amount	Questionnaire	Ph.D student	-	X

*1-2 weeks after admission and before discharge Follow up approx. 6 months after discharge.

** Is handled by physiotherapists with knowledge and skills after the project.

Is handled by the Ph.D student at discharge and admission for depression and quality of life respectively.

Subproject 3. Test- retest reliability of a VO2 peak test

This study includes all patients participating in subproject 1 who are able of performing the test. A seated cross-trainer is used (NuStep T5XR) with an incorporated test protocol in the equipment software. Equipment and protocol is reliable in people with traumatic brain injury and has been validated in healthy persons [32, 33]. In people with an incomplete SCI the equipment is safe, and involves a large amount of muscle mass ensuring completion of the test [34]. The equipment may also be used by patients with a complete SCI of the lower extremities, but in case the equipment is difficult to use for people with a complete tetraplegia, an armcranking ergometer will be used (SCI FIT Pro1). The reliability of the cross-trainer has not previously been evaluated in people with SCI. The test- retest study takes place at discharge, separated by 48 hours or within maximum 5 days at the same time of the day. The participants refrain from caffeine, alcohol and intensive physical exercise on the day of testing as well as tobacco smoking to hours before the test. Bladder emptying is taken care off before the test.

Subproject 4. Test-retest reliability of a multi sensor accelerometer.

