Neurological status: Is determined by the International Standards for Neurological Classification of Spinal Cord Injury (ISNCSCI) and is the most widely used classification in people with SCI [36, 37]. The classification tool involves a sensory and motor examination to determine the neurological level of the injury and whether the injury is complete or incomplete. The ISNCSCI defines neurological level as the most caudal level at which sensory and motor function are intact. The completeness of the injury is graded according to the ASIA Impairment Scale (AIS). AIS is used to determine the degree of motor and sensory function below the level of the SCI. A complete or incomplete injury is defined as absence or presence of sensory and motor function in the most caudal sacral segment. A = complete; B = sensory incomplete without motor function > 3 levels below the motor level of injury on both sides of the body; C = motor incomplete, with preserved motor function below the level of injury and where > 50% of the key muscles below the injury level have a degree < 3 by MMT; D = motor incomplete with preserved motor function below the level of injury and where > 50% of key muscles below the injury level have a degree > 3 by MMT; E = normal sensory and motor function in all segments. ISNCSCI Is already collected as part of the existing routines at CSCI.

Depression: Is measured by the Patient Health Questionnaire- 2 (PHQ-2) which is a generic outcome measure for measuring depression. In people with SCI a cut-off score of 3 is associated with a sensitivity of 83,3% and specificity of 95,7% [38]. PHQ-2 is already collected at admission as part of the existing routines at CSCI

Quality of Life: Is measured by the International SCI Quality of Life Basic Data Set (QoL SCI) which consists of three questions regarding satisfaction with life in general as well as physical and mental health. It is a valid outcome measure with good internal consistency [39] [40]. QoL SCI is already collected at discharge as part of the existing routines at CSCI.

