Data from the patient journals in Epic and the different outcome measures used, is stored in a web based database (Redcap) which is created by the regional Centre for IT, Medico and Telephony (CIMT), with limited access and ID- code, to which pseudo anonymized data is transferred directly,

or via an encrypted USB-stick. An identification list is stored in a locked cabinet at CSCI, local 3403.

Data is stored until December 31, 2027 after which paper material is shredded and data files are deleted.

Statistics

The intervention study and follow up is performed as a pragmatic study and includes, with a few exceptions, all newly injured patients with SCI admitted to primary highly specialized rehabilitation at CSCI. Patients will be included during a time period of 18 corresponding to approximately 40 – 60 patients. Due to the rareness of the morbidity a power calculation is not performed for the primary outcome prior to the intervention, but it is assumed that the total participant number in the intervention and in the historic control cohort, will be comparable to the existing scientific literature.

Numeric continuous data collected at admission, discharge and follow up is reported descriptively as mean and standard deviation together with 95% confidence intervals, or as median, upper and lower quartile as well as interquartile range. Changes over time is reported on the basis of paired t-test. In subproject 3 and 4 the reliability of the outcome measures is analyzed by paired t-test, Pearsons product moment correlation and coefficient of variation or Intraclass correlation coefficient between the test- retest sessions.

Participants, inclusion- and exclusion criteria

Inclusion criteria: All newly injured patients within the previous 12 months, with a SCI and admitted at CSCI are included, regardless of age, neurological level of lesion and completeness of the injury. In subproject 1 all newly injured people with SCI admitted at VCR are also included. Patients under the age of 18 will participate if informed consent is retrieved from their parents.

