Exclusion criteria: Insufficient skills in Danish language and reduced mental function that prevents reading and answering the questionnaires. For the VO₂peak test: Motor complete SCI (AIS A and B) at C4 level or above and assisted ventilatory function. Other exclusion criteria are the presence of decubitus, severe spasticity or musculoskeletal problems considered at risk of aggravation during testing or preventing completion of the test.

Recruitment of participants:

All newly injured patients who are admitted for rehabilitation at CSCI during the project period are included in the intervention (subproject 2) as it becomes a part of usual care during the project period. The Ph.D student is informed about new and future admissions at CSCI by local patient lists every week, and LTPAQ-SCI, ESES, QoL_SCI and NORMON is handed out to the patient and collected again by the Ph.D student. Date and time for the VO₂peak test is handed to the patients physiotherapist, who will make sure to enter it into the patients weekly schedule. The same procedure is repeated at discharge except that QoL_SCI is collected as a part of existing procedures and PHQ-2 is collected by the Ph.D student. In subproject 1, data for VO₂peak at CSCI will only be collected at discharge. All newly injured patients who are admitted for rehabilitation at VCR in the same period are recruited for subproject 1 and data for BMI, SCIM III and ISNCSCI is collected as a part of existing procedures in usual care.

The coordination related to booking of the DEXA-scan and transportation for this is managed by the secretaries. Ordination of the DEXA-scan as well as blood samples related to metabolic profile is handled by the doctors.

Ethical considerations

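### At CSCI the collector of PHQ-2 and QoL SCI changes between admission and discharge, so the paired change in these two secondary outcomes cannot be separated from any collector or setting effect

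*Protocol*

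**What the plan says.** The protocol describes the collection of these two questionnaires at CSCI in three places, and they agree.

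- **Intervention table and footnote.** The method for both measures is a questionnaire. The personnel entry for depression is "Doctors (admission" and for quality of life "Nurses (discharge", each with a mark pointing to a footnote. The footnote covers the other visit: "Is handled by the Ph.D student at discharge and admission for depression and quality of life respectively".
- **Outcome measures.** For depression: "PHQ-2 is already collected at admission as part of the existing routines at CSCI". For quality of life: "QoL SCI is already collected at discharge as part of the existing routines at CSCI".
- **Recruitment of participants.** At admission, "LTPAQ-SCI, ESES, QoL_SCI and NORMON is handed out to the patient and collected again by the Ph.D student"; PHQ-2 is not in that list. The procedure is repeated at discharge "except that QoL_SCI is collected as a part of existing procedures and PHQ-2 is collected by the Ph.D student".

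For the analysis, the Statistics section says: "Changes over time is reported on the basis of paired t-test". It has no term for who collected the data. Outcomes are due at admission, discharge and 6 months after discharge, but no collector of PHQ-2 or QoL SCI is named for the 6-month visit.

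**The concern.** Both instruments are self-reports, one on mood and one on satisfaction with life and with physical and mental health. Answers of this kind can depend on whether the form goes to treating staff as part of care or to a researcher as part of a study. Here that circumstance changes for every CSCI patient between the two visits being compared, and in opposite directions for the two instruments. A reported fall or rise in PHQ-2 or QoL SCI during rehabilitation could then partly reflect the switch.

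This touches planned reporting. The provisional title of the sub project 1 article names depression and quality of life, and that of the sub project 2 article names quality of life. By contrast, LTPAQ-SCI, ESES and NORMON stay with the student at both inpatient visits. The swap follows ward routine; no scientific reason is given for it.

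**Working it through.** The protocol states no figure on this point, so there is none to reproduce. The check has two parts.

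**1. Can time and collector be separated?**

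| Instrument | Admission | Discharge | 6-month follow-up |
|---|---|---|---|
| PHQ-2 | doctors | Ph.D student | not named |
| QoL SCI | Ph.D student | nurses | not named |

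For one instrument, let δ be the true mean change from admission to discharge and γ the shift in score when the student rather than routine staff collects it (γ may differ between instruments). Code time as 0 at admission and 1 at discharge, and collector as 1 for the student.

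- PHQ-2: design rows (intercept, time, collector) are (1, 0, 0) and (1, 1, 1). Three columns, rank 2. The mean paired difference estimates δ + γ.
- QoL SCI: rows are (1, 0, 1) and (1, 1, 0). Three columns, rank 2. The mean paired difference estimates δ − γ.

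Time and collector are fully aliased for both. Because the allocation is the same for every patient, more patients do not help.

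**2. How large would a shift have to be to matter?**

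The sample size of 40 to 60 comes from the Statistics section (intervention cohort). The size of γ is not in the documents, so it is assumed over a range and expressed as d = γ / SD of the change score. With δ = 0, the rejection rate of a two-sided 5% paired t-test is taken from the noncentral t distribution with n − 1 degrees of freedom and noncentrality d√n.

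| Assumed d | n = 40 | n = 50 | n = 60 |
|---|---|---|---|
| 0 | 5% | 5% | 5% |
| 0.1 | 9.5% | 10.7% | 11.9% |
| 0.2 | 23.5% | 28.4% | 33.2% |
| 0.3 | 45.7% | 54.8% | 62.8% |
| 0.5 | 86.9% | 93.4% | 96.8% |

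On the PHQ-2 scale, assume an SD of change of 1.5 points (not in the documents) and n = 50. Then SE = 1.5/√50 = 0.212.

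- γ = 0.3 point (d = 0.3/1.5 = 0.2): t = 0.3/0.212 = 1.41, not significant.
- γ = 0.5 point: t = 0.5/0.212 = 2.36, 49 df, two-sided p about 0.02.
- γ = 1.0 point: t = 1.0/0.212 = 4.71.

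These rows show sensitivity only. They are not estimates of what will happen.

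**The case against.** The strongest reply is that the documents show a change in who handles the form and nothing more. Several parts of it stand.

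- **Interview or mode change.** A reader might infer that patients are interviewed by different people, or that the mode changes. The documents do not support this. The method is listed as a questionnaire, QoL SCI at admission is given to the patient and taken back, and patients unable to read and answer the forms are excluded. How doctors and nurses administer theirs is not stated.
- **Relation between the two measures.** Because the swaps run in opposite directions, a reader might infer that they distort the association between depression and quality of life. A constant shift moves means and leaves correlations unchanged. Distortion would need an effect that varies between patients, and nothing in the documents points to one.
- **Comparison of cohorts.** Sub project 1 serves as the historic control. If both cohorts use the same schedule, the difference in changes is (δ₁ + γ) − (δ₀ + γ) = δ₁ − δ₀, and a constant γ drops out. The protocol sets out no separate schedule for the control cohort, so this is plausible though not stated. The student's part in teaching staff for the intervention could make γ differ between cohorts. The cancellation does not reach the within-patient change, which is the only analysis of change the Statistics section names.
- **Follow-up visit.** If the student collects at 6 months, PHQ-2 from discharge to follow-up and QoL SCI from admission to follow-up would each have a constant collector. The protocol does not say so, and the admission-to-discharge contrast would remain aliased.
- **Scope and pragmatism.** The primary outcome is VO₂peak. These are secondary outcomes at CSCI; the other centre (VCR) supplies only BMI, SCIM III and ISNCSCI. The study is described as pragmatic and relies on existing routines for its completion. All true, and it limits the weight of the point, but keeping the routine does not require using its values for the change score.

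**Conclusion.** The point holds in a limited form. At CSCI, collector and time are fully aliased in the admission-to-discharge change of PHQ-2 and QoL SCI. That follows from the stated schedule and needs no assumption. Whether a bias results, and how large and in which direction, is unknown. The illustration says only that, at 40 to 60 patients, an assumed shift of 0.2 SD of the change score would raise false rejection from 5% to 24–33%, and 0.3 SD to 46–63%.

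It would be too strong to say that the observed change is a collector effect or that the intervention comparison is invalid. It is a measurement inconsistency in two secondary outcomes. It cannot be repaired in the admission-to-discharge contrast once the data are in, and it is easy to prevent.

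**What to change.** Add PHQ-2 at admission and QoL SCI at discharge to the packet that the Ph.D student already gives out and collects, so that both instruments are self-completed under one standard written instruction at both visits. Do the same at the 6-month follow-up and name the collector there. State that only these values enter the analysis of change. Ward collection can continue for clinical use. Apply the same schedule in both cohorts and say so.

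The cost is small: one two-item screener at one visit and three questions at another, with some patients answering the same items twice. The other downside is that the student also helps teach the intervention, which could invite favourable answers. For that reason self-completion should be kept and the student should not read out the items.

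If the schedule cannot be changed, record collector and mode for each form and present the admission-to-discharge change in these two outcomes descriptively, with the aliasing stated.

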Although health promotion related to weight, diet, smoking, alcohol intake and physical activity is part of the usual rehabilitation in CSCI, a systematic approach, follow up and feedback is not provided. Assessment of metabolic profile, body composition and physical capacity is not part of the usual care. In the masterplan for patient care at CSCI, health promoting initiatives are described as "communication and conversation with a health promoting purpose with the patient on a daily basis". How the communication is carried out in practice, and whether some health care professionals have a particular responsibility or expertise related to certain aspects of health promotion eg. based on tests or assessments of health, is unclear and not described in detail. A well described and systematic approach related to health care promotion may ensure that all patients at CSCI receive information and knowledge related to health promotion and the risk of cardiovascular disease.

Sub projects

The project consists of a prospective national survey in collaboration with Spinal Cord Injury Centre of Western Denmark and an intervention at CSCI (see the timeline), which results in 4 sub projects

Sub project 1. Prospective representative national survey of Body Mass Index.

This study includes all patients with a new SCI hospitalized at CSCI or Spinal Cord Injury Center of Western Denmark during a period of 9 months whereby 100 patients are expected to participate. On the basis of usual rehabilitation today, data concerning BMI, level of functioning (SCIM III) and neurological status (ISNCSCI) are collected at admission and discharge. At CSCI BMI is collected every 6 weeks. Also the data for quality of life (QoL SCI), depression (PHQ-2), PA (LTPAQ-SCI) and self-assessed ability to be physically active (ESES) will be collected during this period and at follow up 6 months after discharge. A VO₂peak test at discharge is performed and in some patients measurements of accelerometry (AH) will be performed. Patients with a new SCI who are admitted for rehabilitation several months after the time of injury are also included in the prospective survey. Therefore the data for BMI at the time of injury is collected for all patients at admission to primary rehabilitation from both the patient journal and also by asking the patient about weight and height at the time of injury. Data from this subproject serves as a historic control in the Ph.D project.

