This study includes a subsample of 20 patients participating in subproject 1. The equipment used for monitoring amount and intensity of PA consists of sensors registering acceleration and heart rate and is placed on the thorax of the participant with two surface electrodes. The equipment has previously been used in wheelchair dependent people with SCI, although the reliability of the equipment has not previously been assessed [35]. The precision of the equipment is higher when calibrated individually to the participant using an exercise test [68]. In this project individual calibration will be made during the exercise test described in subproject 3, and continuous measurements of amount and intensity of PA will be made during a period of 24 hours. The test-retest is performed at discharge, separated by 48 hours or within maximum 5 days at the same time of the day.

Outcome measures

All outcome measures will be collected at admission, discharge and follow-up 6 months after discharge. At CSC data for BMI is also collected every 6th week during the hospitalization period.

Primary outcome

Oxygen uptake: Is measured as VO₂peak during a maximal exercise test and is gold standard for measuring aerobic capacity. For people with a SCI several test protocols have been used [36]. The test in this project is performed by using the integrated test protocol in the software of NuStep XR5 or SCI FIT Pro 1. Gradual increments in workload is added every minute depending on the level of lesion. The participant maintains a fixed cadence until predefined criteria for VO₂peak is reached after 8-12 minutes. If VO₂peak is not reached during this period the workload increases each minute until VO₂peak [36, 67]

Secondary outcomes

Objective physical activity: Is measured in a sub-sample in the historic control cohort and the participants in the intervention study with a multisensor device (Actiheart®) recording accelerations and heart rate. It is previously used for wheelchair users with a SCI and individual calibration is important to get the most accurate data [29].

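### VO₂peak is shared by the two cohorts only at discharge, where it is the controls' first protocol test and the intervention patients' second, so any practice gain would favour the intervention

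*Protocol*

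**What the plan says.** VO₂peak is the primary outcome (Outcome measures, Primary outcome): "Oxygen uptake: Is measured as VO₂peak during a maximal exercise test and is gold standard for measuring aerobic capacity".

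**Controls.** Sub project 1 supplies the comparison cohort: "Data from this subproject serves as a historic control in the Ph.D project". Its VO₂peak is placed at discharge in two sections. Sub project 1 says "A VO₂peak test at discharge is performed and in some patients measurements of accelerometry (AH) will be performed", and Recruitment of participants says "In subproject 1, data for VO₂peak at CSCI will only be collected at discharge".

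**Intervention patients.** Outcome measures gives the general schedule: "All outcome measures will be collected at admission, discharge and follow-up 6 months after discharge". Recruitment of participants describes booking the VO₂peak test at admission and adds "The same procedure is repeated at discharge except that QoL_SCI is collected as a part of existing procedures". For the controls, the general sentence conflicts with the two specific statements. Those two agree with each other and are taken as the schedule here.

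**Retest.** Subproject 3 draws on the controls: "This study includes all patients participating in subproject 1 who are able of performing the test". On timing, "The test- retest study takes place at discharge, separated by 48 hours or within maximum 5 days". The Statistics section analyses this pair of tests for reliability and gives it no role in Sub project 2.

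**The concern.** The order of testing differs between the cohorts by design. Usual rehabilitation today states that physical capacity is not assessed in usual care, so the discharge test is the controls' first under the Protocol. For intervention patients it is the second, after the admission test.

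If patients score higher on a second attempt because they know the equipment and the procedure, that gain appears only on the intervention side of a discharge comparison. The paired admission-to-discharge change does not escape the problem, because it too runs from a first test to a second.

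The Protocol says that the cross-trainer's reliability has not been evaluated in people with SCI, so a zero shift cannot be taken for granted. Two control values will exist at discharge for those retested, and the Protocol does not say which one is the historic-control value. If that is left until results are known, the primary outcome is open to selection.

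**Working it through.** **1. Test order, from the text**

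| | Admission | Discharge | Retest, 48 hours to 5 days later | 6-month follow-up |
|---|---|---|---|---|
| Historic controls | none | 1st test | 2nd test (Subproject 3, if able) | none |
| Intervention patients | 1st test | 2nd test | none | 3rd test |

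The only column filled in both rows is discharge, and there the ordinal numbers differ.

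**2. Inputs for size**

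- From the Protocol (Statistics): about 40 to 60 intervention patients, and no power calculation for the primary outcome. There is no stated figure to reproduce.
- From the Protocol (Sub project 1): 100 controls expected over two centres. VO₂peak is described only for CSCI, so the number of controls tested is below 100 and is not given.
- Assumed: two-sided alpha 0.05, no true effect, 30 to 60 controls tested, and a practice gain of d between-patient SDs. The documents give neither d nor the SD.

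**3. Between-cohort discharge comparison**

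Normal approximation, with SE = √(1/n₁ + 1/n₂) in SD units:

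false-positive rate = P(Z > 1.96 − d/SE) + P(Z < −1.96 − d/SE)

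With 50 and 50, SE = √(2/50) = 0.2.

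- d = 0.1: d/SE = 0.5, so P(Z > 1.46) + P(Z < −2.46) = 0.079
- d = 0.2: d/SE = 1.0, so P(Z > 0.96) + P(Z < −2.96) = 0.170
- d = 0.3: d/SE = 1.5, so P(Z > 0.46) + P(Z < −3.46) = 0.323

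With 40 and 40 the rates are 0.073, 0.145 and 0.269. Over 30 to 60 controls and 40 to 60 intervention patients they are 7.0–8.5%, 13–20% and 24–38%.

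To put d on a familiar scale, d = (proportional gain)/(between-patient CV). An assumed 5% gain with an assumed CV of 30% to 50% gives d = 0.17 to 0.10, and with 50 per cohort a rate of about 13% to 8%.

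**4. Paired admission-to-discharge change**

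Here d is in units of the SD of the change. The chance that practice alone yields a significant rise is 1 − Φ(1.96 − d√n). With d = 0.2, n = 40 gives 1 − Φ(0.695) = 0.24, and n = 60 gives 1 − Φ(0.411) = 0.34.

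**5. What the retest can tell**

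The 95% CI for the mean retest-minus-test difference has half-width 1.96/√n in units of the SD of that difference: 0.44, 0.36 and 0.28 for 20, 30 and 50 retested controls (assumed numbers). It estimates the shift with moderate precision.

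If the gain were the same in both cohorts, comparing second test with second test would bring the rate back to 5%. That condition cannot be checked from the planned data, because the gap between tests is a few days in controls and the whole inpatient stay in intervention patients.

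**The case against.** **No between-cohort VO₂peak test is written out.** Statistics lists descriptive summaries, paired t-tests and reliability measures, and the Purpose section ties the historic control to the course of BMI. This stands as a limit: the comparison is inferred from the broader statement in Sub project 1 and from the Designs section calling Sub study 2 controlled. The paired change is written out, however, and has the same order problem.

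**The choice between two control tests belongs in an SAP.** This stands only in part. The unequal test order is fixed by the Protocol's schedule, and any analysis of the discharge values inherits it.

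**The mechanism is not shown.** No section reports a practice effect on this test. Peak criteria set beforehand limit the role of effort, the equipment is described as reliable after traumatic brain injury and validated in healthy persons, and usual rehabilitation includes cardiovascular exercise on unnamed equipment. This stands, so the bias is conditional. A reader might infer that a practice effect is being counted as an intervention effect. The documents do not support that as fact.

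**The estimate is already planned.** Subproject 3's paired t-test gives the retest-minus-test mean difference. True, but nothing links it to Sub project 2.

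**The match is imperfect.** A reader might infer that the retest would remove the bias and so must be the main analysis. The documents do not support that either. The intervals differ greatly, fatigue may lower the retest, and only controls able to be retested contribute, so the swap could under- or over-correct. Which comparison ranks first is a judgement.

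**Testing is part of the intervention.** Sub project 2 uses outcome measures, including physical capacity, to motivate patients. A behavioural effect of feedback from the admission test therefore belongs to the intervention. Familiarity with the equipment does not.

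**Conclusion.** The point holds in conditional form. The schedule sets a second VO₂peak test against a first in the only discharge comparison available with the historic controls, and also in the paired admission-to-discharge change. A practice gain, if there is one, would favour the intervention in both.

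Under assumed inputs (50 per cohort, no true effect, gains of 0.1 to 0.3 SD) the false-positive rate would be about 8% to 32%. The gain, the SD and the number of controls tested are all assumptions, and at zero gain the rate is 5%.

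For the paired change, practice comes on top of ordinary recovery. The Protocol's own background cites a 24% rise in VO₂peak during early rehabilitation, so practice is one of several reasons not to read that change as an intervention effect. The point merits action because data that can inform it are already planned and are given no role here.

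**What to change.** Before the cohorts are compared, add to the analysis section:

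1. Which control test, first or retest, is the historic-control value for VO₂peak.
2. The between-cohort discharge comparison reported both ways: with the controls' first test, and with their Subproject 3 retest (order-matched).
3. The mean retest-minus-test difference with its 95% CI, presented as an estimate of the possible practice shift and used to qualify the admission-to-discharge change in the intervention cohort.
4. The limits: the retest estimates or reduces the bias rather than removing it (days versus a whole inpatient stay, possible fatigue, only controls able to be retested), and behavioural effects of feedback from the admission test count as intervention.

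The general sentence under Outcome measures should also be reconciled with the discharge-only schedule for controls.

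The cost is a few sentences, with no new visits or patients. Controls without a retest drop out of the order-matched comparison. Filling them in as first test plus mean gain would understate the variance unless the uncertainty of that gain is carried through.
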